
Study subjects
	
Subjects in Japan with RCC (not Von Hippel-Lindau disease (VHL)-associated) who have received belzutifan in routine clinical practice for the first time as indicated by the current local label.

Planned subject number
	
403 subjects (safety analysis set)

Study method
	
The study will be conducted with the use of EDC system by means of a central registration method. At each site, subjects that meet the inclusion/exclusion criteria will be approached for informed consent. Subjects may be prospectively identified and registered/enrolled at the time of treatment initiation or retrospectively identified and registered/enrolled after treatment initiation but before the end of the registration period.

Endpoint and its measurement
	
Safety endpoints will include investigator reported adverse events, summarized by frequency and severity, and for secondary effectiveness endpoints, response to treatment by local investigator assessment.

Data Analysis
	
Study endpoints will be analyzed using descriptive statistical methods such as mean, standard deviation, median, interquartile range, and/or minimum/maximum/range for continuous variables. For any categorical variables, e.g., AE analysis, frequency and percentage will be reported. There is no hypothesis testing.
 
To assess whether demographic and/or clinical characteristics impact safety endpoints, these characteristics will be analyzed using descriptive statistical methods and reported for all registered subjects, the safety evaluation group, and presence/absence of AEs/select protocol-specified AEs.
 
Details of the statistical analysis will be specified separately in the statistical analysis plan.

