6.5 Study Method

Procedures and activities during this study are outlined in [Table 1](#).

Table 1 Schedule of Activities

Timing of implementation Item	Before the start of administration	Observation Period (Up to a Maximum of 12 Months)				Note
		During administration	At the end of administration	From the end of administration until 30 days after the end of administration	End of observation phase (12 months)	
Informed consent / Privacy statement	X					
Inclusion/Exclusion criteria review	X					
Subject characteristics and indication(s) for use	X					
Medical history and Concurrent condition	X					For liver dysfunction, The Child-Pugh classification (Table 2) is used. Points are assigned to each item, and the total score is classified based on Table 3 .
Condition of RCC before belzutifan Administration	X					
Prior Treatment for RCC before belzutifan Administration	X					

Timing of implementation Item	Before the start of administration	Observation Period (Up to a Maximum of 12 Months)				Note
		During administration	At the end of administration	From the end of administration until 30 days after the end of administration	End of observation phase (12 months)	
Treatment with belzutifan		X	X			
Concomitant medications/Concomitant therapies		X	X	X		Concomitant medications/therapies for RCC used during belzutifan administration period, and AE/ prophylactic use during the administration period or within 30 days after discontinuation of belzutifan.

Timing of implementation Item	Before the start of administration	Observation Period (Up to a Maximum of 12 Months)				Note
		During administration	At the end of administration	From the end of administration until 30 days after the end of administration	End of observation phase (12 months)	
Effectiveness		X	X	X	X	Effectiveness assessments will be conducted until disease progression, initiation of other anti-cancer therapies, death, or loss to follow-up, whichever occurs first. However , the maximum assessment period will not exceeding the observation period [12 months (52 weeks) from the first belzutifan treatment date].
Status on the date of last observation					X	At 12 months (52 weeks) from the start of belzutifan administration; however, in cases where death or lost to follow-up occurs within 12 months from the start of belzutifan administration, the date of confirmation of these events shall be considered.
Adverse Event		X	X	X		Refer to Table 4 , Table 5 and Table 6 for supplementary notes related to AEs.

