Timing of implementation Item	Before the start of administration	Observation Period (Up to a Maximum of 12 Months)				Note
		During administration	At the end of administration	From the end of administration until 30 days after the end of administration	End of observation phase (12 months)	
Laboratory data/test	X	X	X	X		Laboratory test values and examinations related to AEs will be collected in this survey.

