Concomitant medications	
 • Presence or Absence of concomitant medications 
For any concomitant medications:
 
 • Name of concomitant medication • Daily dose • Route of administration • Duration of medications (Start date and stop date of administration) • Reason for use
Non-pharmacological Concomitant therapies	
 • Presence or Absence of concomitant therapies 
For any concomitant therapies:
 
 • Detail of concomitant therapies (Radiotherapy, Surgical procedure, Other therapy) • Duration of treatment (Start date and stop date of therapy) or date of procedure • Reason for therapies
Effectiveness	
Investigators will assess and report effectiveness as detailed below. Timing of these assessments will based upon routine follow-up evaluations.
 
 • Presence or absence of effectiveness evaluation 
For any effectiveness evaluations:
 
 • Assessment method Assessment methods will follow the standard procedures of each site, including but not limited to Response Evaluation Criteria in Solid Tumors guideline version 1.1 (RECIST v.1.1). Whenever possible, the same assessment method should be used consistently for each individual patient. • Tumor response assessment (Date of assessment, Tumor response)

Category	Collection item
Status on the date of last observation	
 • Last observation date • Condition on the last observation date • Administration status of belzutifan after 12 months of observation following the start of administration • Other treatments for RCC within 30 days after the last administration of belzutifan³ • Date of discontinuation of belzutifan (if applicable) • Reason for discontinuation (if applicable) • Presence or absence of intracranial lesions during the observation period • Occurrence of intracranial hemorrhage up to 30 days after the last dose of belzutifan

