AEs	
 • Presence or Absence of adverse event 
For any adverse event:
 
 • Adverse event term • Onset date • Seriousness • Reason for seriousness • Causal relationship by investigator with belzutifan • Factors other than belzutifan • Maximum Common Terminology Criteria for Adverse Events (CTCAE) grade • Outcome / Date of Outcome • Action taken with belzutifan after the onset of the adverse event • With or without re-administration of belzutifan • Improvement of adverse events after de-challenge of belzutifan • Recurrence of AEs after re-administration of belzutifan • Cause of Death and Autopsy Details (if applicable) • Procedures and laboratory test⁴ data / test details. • Safety Considerations 
[Hemorrhage]
 
 • Site of hemorrhage

³ The total follow-up period will not exceed the observation period [12 months (52 weeks) from the first belzutifan treatment date]

⁴ Clinical laboratory values/tests for anemia (Hb), hypoxia (SpO₂) and hemorrhage (PT, PT/INR, APTT, platelet count)

Category	Collection item
	
 • Volume of hemorrhage (only for intracranial hemorrhage, if applicable) • Comorbidities potentially contributing to hemorrhage • Use of drugs that affect the coagulation system (anticoagulants, antiplatelet agents, and NSAIDs) • Laboratory test [prothrombin time (PT), PT/INR, APTT, Platelet count], if applicable 
[Fracture]
 
 • Site of fracture • Fracture at the metastatic site 
[Anemia]
 
 • Use of erythropoiesis-stimulating agents following the onset of the event. • Use of blood transfusion following the onset of the event. • Laboratory test (Hb) 
[Hypoxia]
 
 • Symptoms/signs observed at the time of onset • Oxygen administration following the onset of the event • SpO₂
Laboratory data (only if related to adverse events)	
 • Name of laboratory test⁵ • Date of laboratory test performed (before the first administration of belzutifan, after the initiation of administration) • Laboratory results

⁵ Clinical laboratory values/tests other than those for anemia (Hb), hypoxia (SpO₂), and hemorrhage (PT, PT/INR, APTT, platelet count)

Category	Collection item

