6.9.3 Secondary Objective analysis

- 1) Patient demographic and clinical characteristics will be analyzed and reported as noted above according to whether they are a categorical or continuous variables for:

- a) the registered subjects
- b) the safety evaluation group
- c) by presence/absence of any adverse event
- d) by presence/absence of hemorrhage
- e) by presence/absence of fracture
- f) by presence/absence of anemia
- g) by presence/absence of hypoxia
- h) by presence/absence of intracranial lesions

- 2) The incidence of anemia AEs and the incidence hypoxia AEs, including all AEs, ADRs, grade 3-5 AEs, grade 3-5 ADRs, SAEs, and SADR will be separately analyzed and reported as categorical variables

- 3) The incidence of intracranial hemorrhage AEs with or without pre-existing intracranial lesions, including all AEs, ADRs, grade 3-5 AEs, grade 3-5 ADRs, SAEs, and SADR reported by the investigator will be separately analyzed and reported as categorical variables
- 4) The incidence of overall safety events reported by investigator, including all AEs, ADRs, grade 3-5 AEs, grade 3-5 ADRs, SAEs, SADR, unexpected SAEs, and unexpected SADR, will be analyzed and reported as categorical variables
- 5) The following will be analyzed and reported as categorical variables for a) hemorrhage AEs, b) fracture AEs, c) anemia AEs, d) hypoxia AEs, e) all AEs, f) all SAEs, g) all ADRs and h) all SADR reported by the investigator:
 - the proportion of subjects who interrupt drug due and the reasons for drug interruption
 - the proportion of subjects who discontinue drug and the reasons for drug discontinuation
 - the proportion of subjects with dose reduction and the reasons for dose reduction
- 6) The following will be analyzed and reported as categorical variables for the effectiveness analysis population based on the investigator's overall assessment after completion of administration, as detailed in the stand-alone statistical analysis plan:
 - ORR: best overall response rate (CR or PR)
 - DCR: best response rate of (CR, PR, SD)

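### Table 1 and Section 6.6 disagree on which concomitant drugs are recorded, so coagulation-active drugs may be captured more fully in subjects with hemorrhage than in those without

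*Protocol*

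**What the plan says.** **Event-triggered items.** In Protocol 6.6, under AEs, the hemorrhage sub-list asks for "Use of drugs that affect the coagulation system (anticoagulants, antiplatelet agents, and NSAIDs" and for "Laboratory test [prothrombin time (PT), PT/INR, APTT, Platelet count], if applicable". Both are completed only when a hemorrhage is reported.

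**Laboratory data in general.** The separate category in 6.6 is headed "Laboratory data (only if related to adverse events". Its footnote restricts it to tests other than Hb, SpO2 and the coagulation and platelet tests. Table 1 marks a column before the start of administration, but its note says "Laboratory test values and examinations related to AEs will be collected in this survey".

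**Concomitant medication.** Section 6.6 has a category not tied to any event. It asks for presence or absence and then, "For any concomitant medications", for name, daily dose, route, dates and reason. The Table 1 note describes a smaller scope: "Concomitant medications/therapies for RCC used during belzutifan administration period, and AE/ prophylactic use during the administration period", extended to 30 days after discontinuation.

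**Planned use.** The synopsis gives the aim as "To assess whether demographic and/or clinical characteristics impact safety endpoints". Section 6.9.3(1)d tabulates demographic and clinical characteristics "by presence/absence of hemorrhage". Section 6.9 counts concomitant medications as patient background.

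**The concern.** Hemorrhage is one of the two risks in the primary objective, and anticoagulants, antiplatelet agents and NSAIDs are the drugs the protocol itself asks about in every bleed. A yes/no comparison is informative for a factor only if the factor is sought in the same way in both groups. Here a subject with a bleed gets a direct question. A subject without one is covered only by a general item whose scope is stated in two ways.

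Under the narrower scope, a subject on long-term therapeutic anticoagulation or an analgesic NSAID who never bleeds need not have the drug entered. These drugs would then look more common in bleeders even if they were not. This is a matter of data collection: a field that was never entered cannot be recovered by the statistical analysis plan.

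**Working it through.** **1. The plan's own figures.** Section 6.3 wants at least 11 Grade 3 or higher hemorrhages with over 90% probability at an incidence of 3.8%. The exact binomial tail P(X ≥ 11) is 0.9005 at n = 403 and 0.8988 at n = 402, so 403 reproduces. The 42 any-grade hemorrhages also reproduce as a 90% lower figure at 12.6%: P(X ≥ 42) = 0.921 and P(X ≥ 43) = 0.895. Nothing in this point changes the sample size.

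**2. Expected split.** With the Study 005 incidence of 12.6% (6.3): 403 × 0.126 = 50.8, about 51 cases. Non-cases: 403 − 51 = 352.

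**3. Where each factor is collected.**

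| Factor | Subjects with hemorrhage | Subjects without hemorrhage |
|---|---|---|
| Coagulation-active drugs | Direct question, plus general item | General item only; scope is any medication (6.6) or RCC and AE/prophylactic use (Table 1) |
| PT, PT/INR, APTT, platelets | Hemorrhage items, if applicable | Not planned, apart from AE-related tests and the prothrombin/INR part of Child-Pugh in hepatic impairment |
| Age, performance status, comorbidities, IMDC risk, metastatic sites | Collected | Collected |

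Only the first two rows are affected.

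**4. Size of the distortion.** Let u be the true use, equal in both groups, and c the fraction of users captured among non-cases, with full capture in cases. Cases show u and non-cases show c × u, so the apparent ratio is u / (c × u) = 1/c. The documents give neither u nor c. Assuming u = 20%, cases show 0.20 × 51 = 10.2, or 20%. Among non-cases there are 0.20 × 352 = 70.4 true users:

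| Assumed capture c | Recorded users among 352 | Non-case column | Apparent ratio |
|---|---|---|---|
| 25% | 17.6 | 5% | 4.0 |
| 50% | 35.2 | 10% | 2.0 |
| 75% | 52.8 | 15% | 1.3 |
| 100% | 70.4 | 20% | 1.0 |

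The last row is what the 6.6 scope would give if it were followed completely. The ratio depends on c alone, neither on u nor on the case count.

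**The case against.** The strongest reply is that drug use is not confined to the hemorrhage items. Section 6.6 has an all-subject medication item with names and dates, and 6.9 plans to summarize concomitant medication. That stands: a reader might infer that these drugs are recorded only once a bleed occurs, and the protocol does not say so. Capture in non-cases is uncertain, not absent. The Table 1 wording on prophylactic use may also cover some long-term antithrombotic treatment.

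A reader might also infer that the hemorrhage yes/no table has no valid non-case column at all. That is not supported. The baseline items, including comorbidities, are collected for every subject, and no text makes the event-triggered fields rows of that table. They can be read as case description, beside site and volume of bleeding. The exact rows may properly be left to the analysis plan.

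Nor is tabulating characteristics by event status an error. With a cases and b non-cases at a given level, incidence at that level is a/(a + b), so the same counts give it wherever the factor is collected in everyone.

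Finally, the study is descriptive, without hypothesis tests, and 6.10 already says that associations cannot be directly evaluated. This limits the consequences. It does not settle which medication scope sites should follow, and 6.10 does not name outcome-dependent collection among its sources of information bias.

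**Conclusion.** The point holds as a contradiction over collection scope with a foreseeable bias, not as a failure of the whole comparison. Table 1 and 6.6 cannot both direct the sites. If Table 1 is followed, and to the extent that its wording leaves out therapeutic use, coagulation-active drugs are captured more fully in bleeders, and a hemorrhage yes/no table showing concomitant medication is biased toward an association. If 6.6 is followed fully, the distortion largely disappears for drugs. Under either scope, the coagulation tests cannot be compared between subjects with and without hemorrhage.

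The direction is clear wherever capture in non-cases is less complete than in cases. The size is not known. The range from no contrast to four-fold rests on assumed capture of 100% down to 25%, with equal true use and full capture in cases. The 51 to 352 split assumes that the Study 005 incidence carries over. Primary hemorrhage and fracture incidence, error rates and the sample size are untouched.

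**What to change.** 1. Align the Table 1 concomitant-medication note with 6.6, so that one scope is stated.
2. Add baseline yes/no fields, taken from the chart, for anticoagulant, antiplatelet and NSAID use in all registered subjects, whether or not an event occurs. Optionally add the latest available platelet count and PT-INR before the first dose.
3. If these fields are not added, keep the event-triggered hemorrhage items out of the 6.9.3(1)d comparison, use them only to describe cases, and name outcome-dependent collection as a limitation in 6.10.

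The cost is a few extra eCRF fields per subject and a small added burden on sites. Section 6.1 already sources patient and treatment data from medical records, so no new tests are needed.

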6.7 Endpoint Measurement

All AEs in the (e)CRFs will be classified into the System Organ Class (SOC) and the Preferred Term (PT) of AE according to the classification of MedDRA (Medical Dictionary for Regulatory Activities).

⁶ The serum bilirubin level is scored as 1 point if it is less than 4.0 mg/dL and 3 points if it is 10.0 mg/dL or higher in cases of cholestasis (PBC).

6.7.1 Primary endpoints

Safety items

The following will be set as endpoints for the risk of hemorrhage and fractures using investigator reported adverse events, including frequency and severity of these events:

- Adverse Events (AEs), Serious Adverse Event (SAEs), Grade 3-5 AEs
- Adverse Drug Reactions (ADRs), Serious ADRs (SADRs), Grade 3-5 ADRs

6.7.2 Secondary endpoints

Safety items

The following will be set as endpoints for the risk of anemia and separately hypoxia using investigator reported adverse events, including frequency and severity of these events:

- AEs, SAEs, Grade 3-5 AEs
- ADRs, SADRs, Grade 3-5 ADRs

The following will be set as endpoints for the risk of intracranial hemorrhage with or without pre-existing intracranial lesions using investigator reported AEs, including frequency and severity of these events:

- AEs, SAEs, grade 3-5 AEs,
- ADRs, SADRs grade 3-5 ADRs

The following will be set as endpoints for overall safety using investigator reported adverse events, including frequency and severity of these events:

- AEs, SAEs, Grade 3-5 AEs, Unexpected SAEs
- ADRs, SADRs, Grade 3-5 ADRs, Unexpected SADRs,

Effectiveness items

The following will be calculated.

- Overall Response Rate (ORR): Complete Response (CR) or Partial Response (PR)
- Disease Control Rate (DCR): CR, PR, or Stable Disease (SD)

6.7.3 Definition of safety related information

Adverse Event (AE)

Any untoward medical occurrence in a patient or clinical investigation subject administered sponsor's product and which does not necessarily have to have a causal relationship with this product. An adverse event can therefore be any unfavorable and unintended sign (including an abnormal laboratory finding, for example), symptom, or disease temporally associated with the use of the product, whether or not considered related to the product. Any worsening (i.e., any clinically significant adverse change in frequency and/or intensity) of a preexisting condition that is temporally associated with the use of the product, is also an adverse event.

Disease progression of "RCC" to be investigated in this study will not be regarded as an AE as long as the investigator judges it to be an expected progression.

Adverse Drug Reaction (ADR)

An AE which has a causal relationship with the product, that is, a causal relationship between the product and the adverse event is at least a reasonable possibility.

Serious Adverse Event (SAE) / Serious Adverse Drug Reaction (SADR)

An adverse event or adverse reaction that results in death, is life threatening, results in persistent or significant disability/incapacity, requires inpatient hospitalization, prolongation of existing inpatient hospitalization, is a congenital anomaly/birth defect, or is another important medical event. Other important medical events that may not result in death, may not be life-threatening, or may not require hospitalization may be considered an SAE/SAR when, based upon appropriate medical judgment, they may jeopardize the patient or subject and may require medical or surgical intervention to prevent one of the other outcomes listed previously. Examples of such medical events include allergic bronchospasm requiring intensive treatment in an emergency room or at home and blood dyscrasias or convulsions that do not result in inpatient hospitalization.

Non-serious Adverse Event (NSAE)

An adverse event that does not meet any of the serious criteria in above 3).

Collection period of adverse event

Adverse events will be collected throughout the treatment period and for 30 days following discontinuation of belzutifan treatment. The follow up period for each subject will vary according to the treatment of belzutifan, but the maximum follow-up period will not exceed the observation period [12 months (52weeks) from the first date of belzutifan treatment.]

6.7.4 Evaluation of adverse event

An investigator who is qualified will evaluate all adverse events with respect to the elements outlined in this section. The investigator assessment of causality is required for each adverse event.

Causality assessment

An investigator who is qualified will assess the causality according to his/her best clinical judgment.

The investigator will use the following criteria as guidance (not all criteria must be present to be indicative of causality to a Sponsor's product) :

- There is evidence of exposure to the Sponsor's product.
- The temporal sequence of the AE onset relative to the administration of the Sponsor's product is reasonable.
- The AE is more likely explained by the Sponsor's product than by another cause.

A causality assessment is the determination of whether or not there is at least a reasonable possibility that a product caused the adverse event.

AE seriousness assessment

An investigator who is qualified will evaluate the seriousness of each AE. SAE is any AE occurring at any dose or during any use of Sponsor's product as shown in [Table 4](#).

Table 4 Criteria for Defining Serious Adverse Events (SAEs)⁷

Results in death	—
Is life-threatening	or places the subject, in the view of the investigator, at immediate risk of death from the experience as it occurred (Note: It does not refer to an event which hypothetically might have caused death if it were more severe); or
Requires inpatient hospitalization or prolongation of existing hospitalization	Hospitalization is defined as an inpatient admission, regardless of length of stay, even if the hospitalization is a precautionary measure for continued observation. (Note: Hospitalization [including hospitalization for an elective procedure] for a preexisting condition which has not worsened does not constitute a serious adverse experience.);
Results in a persistent or significant disability/incapacity	Substantial disruption of one’s ability to conduct normal life functions
Is a congenital anomaly/birth defect	In offspring of subject taking the product regardless of time to diagnosis
Is an otherwise important medical event	Other important medical events that may not result in death, may not be life-threatening, or may not require hospitalization may be considered an SAE/SAR when, based upon appropriate medical judgment, they may jeopardize the subject and may require medical or surgical intervention to prevent one of the other outcomes listed previously. Examples of such medical events include allergic bronchospasm requiring intensive treatment in an emergency room or at home and blood dyscrasias or convulsions that do not result in inpatient hospitalization.

AE severity evaluation

AE severity is assessed based on the worst grade according to CTCAE in collection period of AEs.

The severity of each adverse event (AE) will be evaluated by a qualified investigator.

The definition of severity will follow the CTCAE version 5.0, developed by the U.S. National Cancer Institute (NCI). For Japanese investigators, the Japanese translation provided by the Japan Clinical Oncology Group (JCOG)⁸ will be used as a reference to ensure consistency in interpretation and grading.

⁷ Based on ICH E2A and Japanese regulatory guidance (e.g., MHLW and PMDA)

⁸ The CTCAE v5.0 (JCOG version) is publicly available at: <https://jcog.jp/doctor/tool/ctcae5/>

Definition of severity is listed below in [Table 5](#):

Table 5 CTCAE v5.0 (JCOG version)

Grade 1	Mild; asymptomatic or mild symptoms; clinical or diagnostic observations only; intervention not indicated.
Grade 2	Moderate; minimal, local or noninvasive intervention indicated; limiting age-appropriate instrumental activities of daily living (ADL) ⁹ .
Grade 3	Severe or medically significant but not immediately life-threatening; hospitalization or prolongation of hospitalization indicated; disabling; limiting self-care ADL ¹⁰ .
Grade 4	Life-threatening consequences; urgent intervention indicated.
Grade 5	Death related to AE.

AE expectedness assessment

The Sponsor will assess the expectedness (labeled or unlabeled / listed or unlisted) of each selected AE according to the latest HA’s approved local product circular.

